Space/time needed			1 meeting per week (1-2 hours)		Four meetings total, each 2 hours		1 weekly meeting (1-2 hours) for 4 weeks		Screening space 1-2 days/week per site	Room for intervention 1 X per week at each site for 1-2 hours (same time each week)		
YEAR 2 (2021))											
	21-Jan	21-Feb	21-Mar	21-Apr	21-May	21-June	21-July	21-Aug	21-Sept	21-Oct	21-Nov	21-Ded
PRIMARY ACTIVITIES	Recruit Cohort 2	MBI & HP C2	2		Recruit Cohort 3	MBI & HP C	ohort 3		Recruit Cohort 4	MBI & BP Co	hort 4	
Space/time needed	Screening space 1-2 days/week per site	Room for inte X per week a for 1-2 hours time each we	ervention 1 It each site (same eek)		Screening space 1-2 days/week per site	Room for in X per week for 1-2 hour each week)	Room for intervention 1ScX per week at each sitespfor 1-2 hours (same timedaeach week)pe		Screening space 1-2 days/week per site	Room for intervention 1 X per week at each site for 1-2 hours (same time each week)		
Follow-up	·			Cohort 1 follow- up	·			Cohort 2 follow-up	·		ł	Cohort 3 follow-up
YEAR 3 (2022))											
	22-Jan	22-Feb	22-Mar	22-Apr	22-May	22-June	22-July	22-Aug	22-Sept	22-Oct	22-Nov	22-Dec 23 Jan- Feb
PRIMARY ACTIVITIES	Recruit Cohort 5	MBI & HP Co	phort 5			Recruit Cohort 6-7	MBI	Cohorts 6-7				
Space/time needed	Screening space 1-2 days/week per site	Room for inte X per week a for 1-2 hours time each we	ervention 1 It each site (same eek)			Screening space 1-2 days/week per site	Room for intervention 1 X per week at each site for 1-2 hours (same time each week)					
Follow-up				Cohort 4 follow up		·	Cohort 5 follow up				Cohorts 6 ups	6-7 follow

6 - Basic Definitions

Mindfulness: The process of focusing one's attention on the present moment (including thoughts, feelings, and sensations) without judgement (Kabat-Zinn, 1990; Lang, 2017).

Mindfulness-Based Stress Reduction (MBSR): MBSR is an 8-week, 9 session manualized mindfulness-based intervention that is appropriate for participants from different religious, spiritual, or ethnic background and is not grounded in religious ideology. During MBSR, participants will be trained in mindfulness meditation and the applicability of mindfulness to daily life.

Post-traumatic Stress Disorder (PTSD): PTSD is a psychological pathology characterized by re-experiencing, avoidance, negative thoughts or cognitions, hyperarousal after experiencing a traumatic event.

Trauma: According to the DSM-5, must involve actual or threatened death, serious injury, or sexual violence.

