Arm: The different groups of the intervention. In this study, Arm 1 is the health promotion attention control and Arm 2 is the MBSR. Participants at a given site are assigned to one Arm or the other, by cohort).

Cohort: The group of people that are doing the interventions at the same time.

Cortisol: The body's main stress hormone, triggered by the adrenal glands. Cortisol is a glucocorticoid and is released in the body about 20 minutes after a stressor. The immediate stress response hormones (adrenaline and epinephrine) are released within seconds or minutes; if the brain continues to perceive something as stressful, then cortisol is released.

C-Reactive Protein (CRP): This is a protein made in the liver. CRP tends to increase when there is inflammation occurring in the body, (Lindqvist et al., 2014, 2017) induced by proinflammatory cytokines in the liver (Eklund, 2009). These heightened inflammatory responses can lead to health impairments including atherosclerosis (Wong et al., 2012) and cardiovascular disease (Coughlin, 2011) compounding health disparities in disadvantaged populations; CRP, in particular, has been linked with obesity (Visser et al., 2011) metabolic syndrome (Ridker et al., 2003) and CVD.(Ridker et al., 1998) Thus CRP can be used as marker for general inflammation and risk for inflammatory-related problems.

Other acronyms used in this protocol:

IISBR - Institute for Interdisciplinary Salivary Bioscience Research - https://iisbr.uci.edu/

- IISBR is a shared resource and scientific hub; researchers can gain practical experience/knowledge in salivary bioscience through the training programs (e.g., Spit

Camp). IISBR also provides the storage and analyses of the salivary samples collected in this study.

SECTION 1B. INTRODUCTION TO PTSD AND MBSR

Subsection 1B.1 - PTSD Basics

PTSD Diagnosis

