In Phase II, we will assess the potential benefit of MBSR to reduce PTSD (primary outcomes) and secondary outcomes (e.g., depression, SUD, CRP, cortisol reactivity), among 130 eligible homeless women who exhibit likely subthreshold or threshold PTSD living at one of two residential drug treatment facilities. MBSR will be compared to an attention-control group (Health Promotion Wellness Classes; HP). There originally intended to be five cohorts of women, each with 12-15 women (total of 24-30 women per cohort). However, due to COVID-19 adjustments have been made in terms of the class size and randomization procedure. At each cohort, sites will be randomized to receive either the MBSR or the HP. Although sites will alternate between MBSR and HP by cohort, each participant will receive either the MBSR or the HP. Randomization will occur using RedCAP. The women participate in either MBSR or HP for 9 weeks. Psychosocial data will be collected at baseline, immediately following final intervention session, and at 6-month follow-up via tablet questionnaires. After psychosocial data collection, a stress task (Trauma Imagery Task) will be conducted at each time point, with saliva collected both before and after the task to assay cortisol and CRP. This proposal will improve on the methodological rigor of prior research on MBIs for PTSD in disadvantaged populations by using: randomization procedures that account for cross-contamination; blind evaluators; longitudinal follow-up; an attention control group equal to the MBI intervention in both contact visits and hours; increased demographic diversity; comprehensive lifetime trauma assessment; and inclusion of objective indices of stress responses to accurately evaluate the effectiveness of MBIs in treating trauma-related symptoms.

Confidentiality and Ethical Issues

All program staff must follow confidentiality and ethical procedures throughout this program to ensure that everybody is treated with respect and dignity.

1. Communication with study participants must remain confidential. To maintain confidentiality for participants, any personal information provided, such as participants' name, age, etc., will

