- c. Tablets will be programmed by the Research Director from the School of Nursing and responses will be automatically, electronically scored. All participants who complete the screener will receive \$3.
 - i. Note: those who complete the screener must complete the consent to screen, but are not assigned a participant ID at this time as they have not completed the **Informed Consent**. As such it is imperative that accurate information be obtained with respect to the individual's name as that will be used to link it to their subsequent data.

- 2. Group Assignment and Intervention Procedure (may chance due to evolving circumstances due to COVID-19)
 - a. Prior to recruitment, the Residential Treatment Sites (RTS; Pomona and Escondido) will be randomized to receive the MBI or serve as the attention-control (HP); recruitment and research procedures (MBI or attention-control) will occur at both sites simultaneously. Women will live at sites prior to recruitment.
 - b. Informed consent there are TWO versions of the Informed Consent documents. One is for the MBSR course: the other is for the HP course. Women will complete ONE of the Informed Consent forms, depending on which group they are in. It is imperative that the correct form is filled out and uploaded onto REDCap.
 - c. Baseline questionnaire administered:
 - i. After informed consent, participants will complete a baseline questionnaire. In addition to the traumas indicated in the PCL-5, participants will report lifetime history of trauma (including whether events occurred in adulthood, childhood, or both).
 - ii. Questionnaire data will be collected via tablet and transferred to RedCap.
 - iii. Participants will provide a urine sample for a drug test to validate self-report. Then participants will complete the brief stress (Trauma task providing saliva samples both before and after the task.
 - d. Locator guide: this is a critical part of maintaining contact with our participants. However, they may not be inclined to provide all the information on the first or second meeting. PLEASE TAKE THE PICTURE AT THE TIME OF ADMINISTERING **INFORMED CONSENT.** The rest of the locator guide can be filled out over the course of the study. Given issues with COVID-19, we will start completing the Locator Guide after session 2 or 3. Please see PI or Lab Management Team for further guidance.
 - e. Intervention

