KEY = Urine collected for drug screen = Saliva collected immediately before & 20 min post trauma imagery task ^a Measures: lifetime trauma exposure (+ occurrence in adulthood, childhood or both); demographics ^b Updated adversity history (traumatic & stressful events, including incarceration), PTSD dx ^c Depression, self-report substance use, perceived stress, mindfulness, fidelity/ adherence to program, quality of life													

Subsection 2.4 - Phase II Recruitment & Screening

The study was designed so that recruitment at Pomona would be paced to match that at the Escondido site so that all procedures across sites happen in tandem, thus avoiding history effects; recruitment data will be evaluated weekly to inform pacing. Site staff at Prototypes will assist with participant recruitment, informing Prototypes residents of the opportunity during formal announcements during programing. Recruitment flyers will also be posted around the RTS. RAs will help recruit women and conduct the initial screening in a private room after obtaining informed consent; progress will be monitored closely by [name] the Lab Management team. Modifications will be made to allow for the study to continue during the COVID-19 pandemic to ensure safety of Ras, site staff, and participants.

Ideally, recruitment will be staggered according to cohorts and paced equally across sites. In total, five cohorts of women will be recruited. Each will have approximately 26- 28 women in each group/site (n=13-14 MBSR; n=13-14 attention control); recruitment proceeds for one month, the intervention runs for approximately 2 months (9 weeks), then there is one month break. *However, this schedule may vary due to COVID-19 restrictions, limitations, and other feasibility issues*.

[name] will explain the study during an initial meeting with potential participants and answer any questions. Then women will be screened for eligibility. Prior to obtaining any data, the women will provide a "consent to screen". This is because we need to obtain data from the women to determine if they are eligible, but they are not officially enrolled as human subjects. By providing their "consent to screen", we are obtaining verbal consent/permission to ask them questions. Their data will not be used by the research team if they are not eligible.

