All analyses were conducted using STATA 18. First, descriptive statistics were calculated for the total sample. Next, a series of multilevel models were conducted for each primary and secondary outcomes using a multilevel, random-intercept mixed. Participants were entered as random effects to nest observations within participants, allowing for correlations within each individual over time. Group assignment (i.e., MBSR vs. HP Control), time (i.e., T1, T2, and T3), and group-by-time interactions were entered as fixed effects. Site was also included as a fixed-effect, given the low number (i.e., two) of sites¹. Covariates were screened for inclusion in bivariate analyses and included if statistically significant and theoretically meaningful. An independent covariance pattern was specified as our final models were random-intercept (nested within participant) only². Results are presented using restricted maximum likelihood for optimal control of Type 1 error³. An intention-to-treat analysis was conducted, where every participant was included in the final analyses, regardless of whether they completed all of the sessions.

Bibliography

- 2. Weise RE. *Modeling Longitudinal Data*. 1st ed. Springer; 2005.
- 3. Luke SG. Evaluating significance in linear mixed-effects models in R. *Behav Res Methods*. 2017;49(4):1494-1502. doi:10.3758/s13428-016-0809-y

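### Sites are randomised within cohort, but the SAP adjusts for site and omits cohort, and the protocol leaves the number and pairing of cohorts unsettled

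*Combined protocol and SAP*

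**What the plan says.** **Allocation.** Section 2.1: "At each cohort, sites will be randomized to receive either the MBSR or the HP". The definition of an arm under Basic Definitions agrees: "Participants at a given site are assigned to one Arm or the other, by cohort". Section 2.2 adds that "recruitment and research procedures (MBI or attention-control) will occur at both sites simultaneously", and Section 2.4 gives the purpose of the pacing: "all procedures across sites happen in tandem, thus avoiding history effects".

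**Number and size of cohorts.** Section 2.4: "In total, five cohorts of women will be recruited". It continues: "Each will have approximately 26- 28 women in each group/site". The bracket that follows gives 13-14 women per arm, so 26-28 is the size of a cohort. Section 2.2 also says five. Section 2.1 presents five as the initial intention and says that COVID-19 led to changes in class size and randomisation, but gives no new count, size or rule. The Year 3 (2022) calendar has an entry "Recruit Cohort 6-7".

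**Arms in the calendar.** The cells for cohorts 2 to 5 name both arms, with HP garbled at cohort 4. The cell for cohorts 6-7 shows MBI only (the MBSR arm) in the extracted text.

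**Analysis.** The SAP has group, time and group-by-time as fixed effects and a random intercept for participant only. On design factors it says: "Site was also included as a fixed-effect, given the low number". Cohort is not mentioned. It could enter only through the bivariate screening of covariates.

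**The concern.** Arm is fixed by site and cohort together. Randomising within cohort and running both sites at once is the protocol's own protection against calendar time, in a trial whose recruitment and follow-up run through changing COVID-19 conditions. The SAP carries one of the two allocation factors into the model and drops the other.

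With both arms present in equal proportion in every cohort, the design supplies the protection and the model does not need to. The documents do not confirm that this happened. Five cohorts became seven in the calendar. Cohorts 6 and 7 share one recruitment slot and one intervention slot, although the protocol defines a cohort as the women taking the intervention at the same time. So one cannot tell whether 6-7 is one block, two paired blocks or two unpaired classes. If arm proportions differed by cohort, the group-by-time effect would mix treatment with period.

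**Working it through.** **1. The plan's own figures.**

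- Section 2.16: 448 × 0.30 = 134.4, which reproduces the stated 134.
- Section 2.4: 5 × 26 = 130 and 5 × 28 = 140, so 134 fits five paired cohorts.
- Section 2.16: 134 × 0.90 = 120.6 (stated 120), and 120 × 0.80 = 96.
- Seven cohorts of 26-28 would give 7 × 26 = 182 to 7 × 28 = 196. With 134 women, seven paired cohorts mean 134/7 = 19.1 per cohort and 134/14 = 9.6 per class.

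So 134 women, cohorts of 26-28 and seven paired cohorts cannot all be current. No alpha, power, SD or intraclass correlation is stated, so no power calculation can be reproduced.

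**2. What the SAP model passes into group-by-time.** Let *d* be the difference in mean change from baseline between the late cohorts and the rest, the same in both arms. Let *a1* and *a0* be the shares of MBSR and HP women who belong to the late cohorts. With complete data:

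bias in group-by-time = *d* × (*a1* − *a0*)

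| Cohorts 6-7 | Classes MBSR:HP | 134 women split | *a1* − *a0* |
|---|---|---|---|
| Paired, equal | 7:7 | 67:67 | 0 |
| One MBSR class each, no HP | 7:5 | 78:56 | 2/7 = 0.286 |
| MBSR at both sites, no HP | 9:5 | 86:48 | 4/9 = 0.444 |

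A generalised least squares calculation of the SAP model's expectation gives the same 0, 0.286 and 0.444. It assumes 11 women per class, within-person correlation 0.5, complete data, and sites alternating arms in cohorts 1 to 5.

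The kind of shift matters. A constant difference in level between late and early cohorts, present at all three times, moves the arm main effect by 0.29 (7:5) or 0.45 (9:5) per unit and group-by-time by 0. Only a difference in *change* reaches group-by-time.

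**3. Size.** The shift is an assumption. For 0.1 to 0.5 SD:

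- 7:5: 0.1 × 0.286 = 0.03 SD to 0.5 × 0.286 = 0.14 SD
- 9:5: 0.1 × 0.444 = 0.04 SD to 0.5 × 0.444 = 0.22 SD

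**4. Which terms remove it.** Entries are the share of a change shift passed to group-by-time, then the standard error of group-by-time at T2 in SD units.

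| Cohorts 6-7 | SAP model | + cohort | + cohort and cohort-by-time |
|---|---|---|---|
| Paired, equal | 0; 0.161 | 0; 0.161 | 0; 0.161 |
| 7:5 | 0.286; 0.177 | 0.286; 0.177 | 0; 0.191 |
| 9:5 | 0.444; 0.168 | 0.444; 0.168 | 0; 0.191 |

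The standard errors can be checked by hand. At correlation 0.5 the variance of change is 2 × (1 − 0.5) = 1, so SE = √(1/n1 + 1/n0). For 7:5, n1 = 7 × 11 = 77 and n0 = 5 × 11 = 55, giving 0.177. With both cohort terms only the five paired cohorts count, 55 against 55, giving 0.191. The increases are 0.191/0.177 = 1.08 and 0.191/0.168 = 1.14.

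A cohort main effect alone leaves group-by-time exposed. The interaction is what puts the contrast within the block.

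**5. Degrees of freedom.** With *k* cohorts and three times, the terms use (*k* − 1) + 2(*k* − 1) = 3(*k* − 1): 12 for five cohorts, 18 for seven. The planned data are 134 + 120 + 96 = 350 observations, but these are repeated measures from 10 to 14 classes. At class level, after the mean, cohort, site and arm, there remain 10 − 1 − 4 − 1 − 1 = 3 or 14 − 1 − 6 − 1 − 1 = 5.

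**The case against.** A reader might infer that cohorts 6-7 ran MBSR alone and that arm is therefore confounded with calendar time. The documents do not support that. The calendar is visibly damaged: cells are split and letters are wrong throughout the row. The cohort 6-7 entry breaks exactly where HP would stand, and the row beneath still books a room at both sites. Every prose description has two arms running together, and no text announces a single-arm phase. The second copy of the protocol repeats the same garbling, so it is not independent confirmation.

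A reader might also take five against seven as a plain contradiction in trial size. Section 2.1 partly explains it, and smaller classes across more cohorts are consistent with 134 women. No passage plans seven cohorts of 26-28. Nor can a false-positive rate be given, because that needs a standard error for the PCL-5 contrast that the documents do not contain.

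It is also fair to say that paired, balanced cohorts give no bias with or without the term, and that harm to group-by-time needs both unequal arm shares and a period difference in change. The allocation rule itself is not settled: Section 2.2 can be read as one randomisation of sites before recruitment, and Section 2.1 also says that the sites alternate. Finally, the cost is more than 18 degrees of freedom out of 350 suggests, because there are so few classes.

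All of this limits the size of the point. What stands is that the protocol makes cohort the block, the SAP leaves it out without a reason while keeping site, Sections 2.2 and 2.4 still say five, and nothing states how cohorts 6-7 were assigned.

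**Conclusion.** The concern holds as a mismatch between allocation and analysis, not as demonstrated confounding. Under the within-cohort rule of Section 2.1 and Basic Definitions, the model should compare arms within cohort, and it does not.

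The bias is zero if all cohorts ran both arms in equal proportion. Otherwise group-by-time takes up the difference in arm shares times any period difference in change from baseline. The 0.29 to 0.44 range applies only if cohorts 6-7 were MBSR only with equal classes, and the 0.03 to 0.22 SD range also needs the assumed shift of 0.1 to 0.5 SD. Both are illustrations. The change is worth making because it follows the trial's own allocation and removes dependence on an unconfirmed fact.

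**What to change.** **SAP.** Add cohort and cohort-by-time as fixed effects beside site in each primary and secondary model, and say that cohort is included because sites were randomised within it. Do not leave cohort to significance screening, and do not stop at a cohort main effect.

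**Protocol.** In Sections 2.1, 2.2 and 2.4, state one allocation rule, the actual number of cohorts and the class sizes, and reconcile these with the calendar. State whether HP ran in cohorts 6-7 and whether they form one block or two. If HP did not run, base the primary comparison on the cohorts in which both arms were randomised. The two cohort terms already do this for group-by-time, since a single-arm cohort then adds nothing to that contrast.

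**Cost.** The terms use 12 to 18 fixed-effect degrees of freedom. Under the working assumptions the standard error does not change if cohorts are paired and rises by about 8% (7:5) or 14% (9:5) if they are not. With 10 to 14 classes, any class-level inference would have few degrees of freedom left. The SAP is written in the past tense, so if the models have been fitted they must be refitted. Show the existing specification alongside the new one.
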